## **Hypotheses**

Well-differentiated NETs, with positive expression in the MIBG-I scintigraphy exam, will obtain significant radiological, symptomatic and biochemical control, and improved quality of life with therapeutic MIBG-I, which may be a treatment option instead of expensive, toxic and ineffective treatments, such as chemotherapy regimens, interferon alpha and/or liver debulking surgery.

## **Objectives**

### **Primary:**

- 1 - Control of radiological disease at 6 months after the end of treatment.
- 2- Control of clinical/biochemical (functional NET) at 6 months after the end of treatment.

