Adult patients, ECOG 0-2, with good organic functions, with progressing metastatic or locally advanced NET of GI or lung origin, with refractory disease or intolerant to available standard therapies, and with positive MIBG-I scintigraphy in metastatic lesions are eligible for receive up to 4 doses of 7,400Mbq (200 mCi) each, with an interval of at least 60 days. The primary outcome will be the disease control rate (DCR) at 6 months after the end of treatment, per RECIST 1.1; secondary outcomes will be DCR at 3 months post treatment, progression-free survival, radiological and biochemical response (functional NET), toxicities and quality of life measured by the EORTC QLQ-C30 and GINET21 questionnaires. Laboratory tests and clinical evaluation will be performed every 2 weeks during the study; Imaging exams will be performed every 3 months until progression. The study sample will be 22 patients. For this calculation, we consider the H0 of DCR in 6 months of 40% (placebo arm of phase III studies in TNE), H1 as 67%. Two-tailed type I error margin of 10%, power of 80% and loss of follow-up/non-adherence of 10% were considered. We estimated a 50% screening failure (50% positivity on MIBG-I).

If the study is positive, it can be cost-effective, as we estimate that 67% of patients will obtain disease control lasting at least 12 months, which will provide time free of toxic therapies with a low level of evidence and costly to patients and paying sources. In addition, the study has the potential to change the treatment guidelines for NET, facilitating the incorporation of MIBG-I as a therapeutic strategy in the treatment protocols for NET at A.C.Camargo Cancer Center. The study, therefore, may allow the institution in the future to offer treatment with MIBG-I to patients with supplementary health, recovering the costs invested in the MIBNET study.

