## **Outcomes**

### **Primary:**

Disease control rate (DCR). Defined by absence of radiological progression in conventional imaging examinations by RECIST 1.1 at 6 months after the end of treatment. For patients with functioning syndrome, beside radiological DCR, patients should have improved in at least 10% of the baseline score of quality-of-life (EORTC QLQ-GINET21) and stability or decrease in tumor markers.

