### **Statistical plan**

Descriptive statistics will be used to report population characteristics, binary outcomes and adverse events. The Kaplan-Meier method will be used to report time-to-event variables and the reverse Kaplan-Meier method will be used to calculate the follow-up time for patients. For the analysis of quality of life, we will report the proportion of patients who increase the sum of the total score by at least 10% at 3 and 6 months after treatment - improvement of at least 10% is considered to be clinically significant by patients. We will also evaluate whether the global score varies and how much varies during the study for each patient; this analysis will be carried out in percentage and descriptively. The scores will be calculated according to the instruction manual of the EORTC group. The quality-of-life analysis will be carried out using the

intention to treat method, where patients who do not respond will be considered “non-responders” in terms of the effectiveness of the treatment.

Missing data in the questionnaires will be dealt with as described in the section above "Quality of Life Assessment".

The study sample will be 22 patients. For this calculation, we considered the 40-month disease control rate H0 to be 40% (placebo arm of phase III studies in TNE, such as the RADIANT417 study), H1 to 67%. Two-tailed type I error margin of 10%, power of 80% and loss of follow-up / non-adherence of 10% were considered.

We estimated a 40% screening failure (40% positivity on MIBG-I131).

All analyzes will be by intention to treat. Patients who receive at least one dose of MIBGI131 will be evaluated for toxicity and efficacy.

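### The 6-month primary endpoint is defined inconsistently (RECIST-only, a composite for functional tumours, and two listed objectives), and the single error rate is not tied to any one definition.

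*Combined protocol and SAP*

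**What the plan says.** Four sections bear on the primary endpoint.

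- **Abstract.** "The primary outcome will be the disease control rate (DCR) at 6 months after the end of treatment, per RECIST 1.1". No condition is added for functional tumours. The hypotheses follow: "we consider the H0 of DCR in 6 months of 40% (placebo arm of phase III studies in TNE), H1 as 67" per cent.
- **Objectives, Primary.** Two numbered items: "Control of radiological disease at 6 months after the end of treatment", and separately "Control of clinical/biochemical (functional NET) at 6 months after the end of treatment".
- **Outcomes, Primary.** One disease control rate (DCR), based on absence of RECIST 1.1 progression, with an addition: "For patients with functioning syndrome, beside radiological DCR, patients should have improved in at least 10% of the baseline score of quality-of-life" on the GINET21, together with "stability or decrease in tumor markers".
- **Statistical plan.** One null, one alternative and one error rate: "Two-tailed type I error margin of 10%, power of 80% and loss of follow-up / non-adherence of 10% were considered". These are attached to a disease control rate whose definition is not given. Binary outcomes are to be reported descriptively. No test, cut-off, hierarchy or alpha split is stated.

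No section says which definition takes precedence. The Abstract and the section on global innovation potential both describe what follows if the study is positive, so a verdict is intended.

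**The concern.** A patient with a functioning tumour who has no RECIST progression, but whose GINET21 score does not improve by 10% or whose marker rises, is a success in the Abstract and a failure in the Outcomes section. Objective 2 fits neither exactly. It speaks of control, whereas the Outcomes section requires improvement in quality of life, and as listed it does not depend on radiological control.

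The trial is single-arm with 22 patients, so a few such patients could decide the result. With no precedence rule, the definition could be chosen with the results in view, and the stated error rate would then not describe the decision actually made.

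**Working it through.** **1. The plan's own figure.** Inputs from the Abstract and Statistical plan: p0 = 0.40, p1 = 0.67, two-tailed 10% (z = 1.645), power 80% (z = 0.842), loss 10%.

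n = [(1.645 × √(0.40 × 0.60) + 0.842 × √(0.67 × 0.33)) / 0.27]² = [(0.806 + 0.396) / 0.27]² = 19.8.

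19.8 / 0.9 = 22.0, and 20 × 1.10 = 22. (Rounding up to 20 first and dividing by 0.9 gives 23.) The stated 22 is therefore reproduced as the size for one binary endpoint and one test.

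**2. Two measures, one ordering.** Let X be the controlled non-functional patients, Y the controlled functional patients, and W those among Y who also meet the GINET21 and marker conditions. RECIST-only successes are X + Y and composite successes are X + W. Since W ≤ Y, the composite count is never higher.

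**3. The boundary.** With n = 22 and p0 = 0.40:

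| Successes | Exact upper tail | Score z = (x/22 − 0.40) / √(0.24/22) |
|---|---|---|
| 12 | 0.121 | 1.39 |
| 13 | 0.055 | 1.83 |
| 14 | 0.021 | 2.26 |

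A score test at two-tailed 10% (critical value 1.645) is positive from 13. An exact test with at most 5% in the upper tail is positive from 14. Under either rule, one functional patient who counts as a success by one definition and not by the other can reverse the verdict. The choice of test can also reverse it at 13.

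**4. How often the definitions disagree.** Take true radiological DCR 67%, f functional patients out of 22, and probability q that a controlled functional patient also meets the added conditions. Then X ~ Bin(22 − f, 0.67), Y ~ Bin(f, 0.67) and W given Y ~ Bin(Y, q). For cut-off c, P(conflict) = P(X + Y ≥ c) − P(X + W ≥ c). By exact enumeration:

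| f | q | RECIST-only positive (c = 13) | Composite positive (c = 13) | Conflict (c = 13) | Conflict (c = 14) |
|---|---|---|---|---|---|
| 2 | 0.9 | 84.5% | 83.0% | 1.5% | 2.1% |
| 6 | 0.8 | 84.5% | 74.2% | 10.3% | 13.4% |
| 8 | 0.6 | 84.5% | 52.1% | 32.4% | 37.2% |
| 11 | 0.5 | 84.5% | 25.6% | 58.9% | 58.5% |

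The documents give neither f nor q. The rows are assumptions chosen to show the spread and are not bounds.

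**5. Two primary objectives.** Suppose each were tested with 5% in the upper tail and either one sufficed. Under a bivariate normal approximation, the chance of at least one false success is 1 − 0.95² = 0.0975 at correlation 0, 0.088 at 0.5 and 0.068 at 0.9. If both had to succeed, the rate would not exceed 5%.

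**The case against.** The best defence is that the Outcomes section governs. It is the only place that defines the endpoint in full. The 3-month material follows the same pattern: the secondary objectives list radiological and clinical/biochemical control separately, and the secondary outcomes fold them into one composite. The two primary objectives then look like components of one outcome, with the Abstract as shorthand.

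This is a reasonable reading, and part of it stands. There are two measures rather than three, because the Abstract's RECIST-only rate is the same as objective 1. It does not settle the matter, because no section says the composite governs, objective 2 does not match its wording, and the Statistical plan does not say which rate it was sized on.

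A reader might infer that the trial has two chances to succeed and that its error rate is therefore nearly double the stated one. The documents do not support that. No section says either objective alone suffices, and none gives a null or a test for objective 2. Even on that reading the normal approximation is rough at this size. In simulations with a 40% null for both objectives, latent correlation 0.5, and an upper tail of at most 5% for each (14/22 for radiology), the combined rate is 0.060, 0.069, 0.048 and 0.037 with 6, 8, 11 and 14 functional patients. Two of these four stay within 5%.

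It is also fair to say that the size of the conflict depends on unknown inputs and is small if few functional patients enrol.

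**Conclusion.** The inconsistency is real and should be resolved before any outcome data are reviewed. The sample size of 22 is not itself in error: it reproduces for one test. What is missing is the link between that test and one endpoint definition.

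The consequence ranges from negligible to serious. At a true radiological DCR of 67% and a cut-off of 13/22, opposite verdicts arise in about 1.5%, 32% or 59% of trials for the assumed pairs of 2 functional patients with 90%, 8 with 60%, and 11 with 50%. The direction is certain: the composite is never the more favourable of the two. An upper-tail error of about 7–10% instead of 5% would follow only from an either-suffices rule, which the plan does not state.

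**What to change.** State one primary definition in identical terms in the Abstract, Objectives, Outcomes and Statistical plan. Name one test at the stated two-tailed 10%, give the minimum number of successes out of the analysed number, and say that only this test decides whether the study is positive. Make the other version secondary and descriptive, with a confidence interval. In the same edit, reconcile the time point: the Statistical plan labels the 40% as a 40-month rate and the Abstract as a 6-month rate.

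The choice of definition is the sponsor's.

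- **RECIST-only** fits the stated null best, because the example source named in the Statistical plan is titled in the References as a study of non-functional tumours.
- **The composite** has a claim too. The Hypotheses include symptomatic and biochemical control, and the inclusion criteria admit functional patients on clinical and biochemical progression. If it is kept, justify 40% and 67% for it and restate the power.
- **Both objectives as primary** requires a statement that both must succeed, or a split of the 10% with a null for the second.

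The first option costs wording in four sections, with no new patients, visits or data. The composite may also need a revised sample size. In either case the version not chosen loses primary status and cannot by itself make the study positive.

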### **Secondary:**

- 1- Control of radiological disease at 3 months after the end of treatment.
- 2- Control of clinical/biochemical (functional NET) at 3 months after the end of treatment.
- 3- Progression-free survival.
- 4- Radiological response and duration of response.
- 5- Biochemical response in patients with functional NET.
- 6- Evaluate tolerability and quality of life.

## **Outcomes**

### **Primary:**

Disease control rate (DCR). Defined by absence of radiological progression in conventional imaging examinations by RECIST 1.1 at 6 months after the end of treatment. For patients with functioning syndrome, beside radiological DCR, patients should have improved in at least 10% of the baseline score of quality-of-life (EORTC QLQ-GINET21) and stability or decrease in tumor markers.

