All adverse effects will be graded and assessed whether or not they are related to treatment. If there is no CTCAE 5.0 classification for an adverse event, the degree of severity of mild, moderate, severe and life threatening will be used.

An adverse event for the purposes of this protocol is the appearance of (or worsening of pre-existing) undesirable sign(s), symptom(s) or medical condition(s) that occurs(s) after signature. informed consent, even if the event is not considered to be related to the drug(s) under study. The occurrence of adverse events should be obtained through indirect questions asked to the patient at each visit during the study. Adverse events can also be detected when they are reported voluntarily by the patient during or between visits or through physical examination, laboratory tests or other assessments.

Whenever possible, each adverse event should be assessed to determine:

1. Severity (mild, moderate, severe and life threatening) or (CTCAE 5.0 grade)
2. Its relationship to each drug under study (suspected / not suspected)
3. Its duration (initial and final dates or if they continue in the final exam)
4. Conduct adopted (no conduct adopted; study drug dosage adjusted/ temporarily interrupted; study drug permanently discontinued due to the referred adverse event; concomitant medication administered; non-drug therapy administered; hospitalization / prolonged hospitalization).

Patients requiring hospitalization should be immediately identified by the investigators in the study who monitor all patients.

*Criteria suspension of treatment:*

Patients may interrupt study treatment for one or more of the following reasons:

- Disease progression (documented by images and defined by the RECIST 1.1 criteria).

Clinical progression, based on the investigator's assessment

- Death.
- Intolerable or persistent adverse event (s) of grade 2 or higher.
- Withdrawal of consent by the patient.
- Need for new cancer therapy and / or surgery.

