#### Effectiveness and Follow-up Assessments:

For evaluation of efficacy, patients will undergo imaging tests (chest, abdomen and pelvis tomography or abdomen and pelvis resonance) at baseline (within 8 weeks of starting treatment) and every 12 weeks (+/- 5 days) until progression or withdrawal from the study. Patients will also be evaluated for signs and symptoms that may be related to disease progression. Patients who present clinical progression, according to the investigator's judgment, but without radiological progression, will be able to discontinue the treatment and continue the image evaluation until progression; however, if new treatment is instituted, the last date of receipt of MIBG-I will be the censorship date in the progression-free survival analysis.

After documenting progression or leaving the study for other reasons, patients will be followed up by the investigator or another oncologist from the Clinical Oncology team for symptom control, image monitoring and possible future therapies. The patient continues to be cared for at the A.C.Camargo Cancer Center, if desired.

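### The disease control rate has no rule for new anticancer therapy started before the assessment; read literally, such a patient with a non-progressing scan counts as controlled by MIBG

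*Combined protocol and SAP*

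**What the plan says.** **Endpoint.** Under Outcomes, Primary, the DCR is "Defined by absence of radiological progression in conventional imaging examinations by RECIST 1.1 at 6 months after the end of treatment". For functioning syndrome it adds that "patients should have improved in at least 10% of the baseline score of quality-of-life (EORTC QLQ-GINET21) and stability or decrease in tumor markers". The first secondary outcome repeats both parts at 3 months. New anticancer therapy appears in neither definition.

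**Stopping and later treatment.** The criteria for suspending treatment include progression judged clinically by the investigator and "Need for new cancer therapy and / or surgery". Under Effectiveness and Follow-up Assessments, patients with clinical but not radiological progression "will be able to discontinue the treatment and continue the image evaluation until progression". The same sentence goes on: "however, if new treatment is instituted, the last date of receipt of" MIBG "will be the censorship date in the progression-free survival analysis". This is the only rule on new treatment in the protocol, and it names PFS alone.

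**Analysis set.** The Statistical plan says "All analyzes will be by intention to treat" and that patients given at least one dose are evaluated for efficacy. Its non-responder rule is written for the quality-of-life analysis and does not mention later therapy.

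**Design.** One arm, one stage, 22 patients, DCR of 40% under H0 and 67% under H1.

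**The concern.** The protocol foresees that some patients will stop MIBG and move to other treatment before RECIST progression. It sees that this matters for PFS, but leaves the primary endpoint without a rule. Take a patient with a non-functioning tumor who stops early, starts chemotherapy or has hepatic debulking (both named in the Introduction as options after standard treatment fails), and has a stable scan 6 months after the end of treatment. That patient meets the primary definition as written. The clock starts at the end of MIBG treatment, so the other therapy can have up to 6 months to act before the scan.

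No concurrent arm shares this misclassification, and it works in one direction: it can turn a patient not controlled by MIBG into a success, never the reverse. With 22 patients, one or two such cases could decide how the trial is read. If the rule is chosen after the data are seen, that choice could settle the result.

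**Working it through.** **1. The plan's own figure.** Inputs from the Statistical plan: p0 = 0.40, p1 = 0.67, two-sided alpha 10% (z = 1.645), power 80% (z = 0.842), 10% loss. The Abstract places H0 at 6 months.

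n = [z(0.95)·√(p0·q0) + z(0.80)·√(p1·q1)]² / (p1 − p0)² = (0.806 + 0.396)² / 0.27² = 19.8, so 20. Adding 10% gives 20 × 1.10 = 22, the stated size. A rule for new therapy leaves these inputs alone, so N stays at 22. What changes is who counts as a success.

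**2. Effect of one patient.** 1/22 = 4.5 points; 2/22 = 9.1 points, about a third of the 27-point gap between H0 and H1 (9.1/27 = 0.34).

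**3. Effect on the chance of a high count.** Suppose control due to MIBG alone is exactly 40%. Let f be the share of the remaining 60% who start other therapy before RECIST progression and then have a non-progressing scan. The observed rate is p = 0.40 + 0.60·f. Exact binomial tails at n = 22:

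| f (assumed) | p | Expected reclassified, 22 × 0.60 × f | P(X ≥ 13) | P(X ≥ 14) |
|---|---|---|---|---|
| 0 | 0.400 | 0 | 5.5% | 2.1% |
| 3% | 0.418 | 0.4 | 7.8% | 3.2% |
| 5% | 0.430 | 0.7 | 9.6% | 4.2% |
| 10% | 0.460 | 1.3 | 15.4% | 7.4% |

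The plan states no success threshold. At n = 22, 14 is the smallest count whose upper tail under 40% is at most 5%, and 13 just exceeds it at 5.5%; both are shown for that reason.

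**4. Where f might lie.** The documents do not give it. Table 1 offers some anchors. If 30% of failures (assumed) received chemotherapy and 10% of those were controlled (the top of the table's range), f = 0.30 × 0.10 = 3%. The table gives 50% radiological control for interferon, so f = 10% would need 0.10/0.50 = 20% of failures to start it before RECIST progression.

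**5. The two endpoints side by side.** A patient starts new therapy without RECIST progression and later has a stable scan. In PFS, follow-up is cut at the last MIBG date. In the DCR, the only test is the scan, so the patient is controlled. If the patient is instead taken to have left the study and has no 6-month scan, PFS still has its rule and the DCR has none.

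**The case against.** The strongest reply is that this is silence, not a rule. A reader might infer that the plan declares such a patient a success; no sentence does. The result comes from a literal definition together with a missing exception.

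A reader might also infer that the 6-month scan is sure to exist. That is not settled. Study design ends imaging at progression or exit from the study, and the follow-up section mentions future therapies after progression or leaving for other reasons. New therapy could fairly be read as leaving. This stands, but it only exchanges one gap for another, because the DCR does not say how a patient without that scan counts.

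A third tempting inference is that stopping for clinical progression should itself be a failure. The documents do not support that. The first primary objective is radiological control, clinical and biochemical control is required only for functional NET, and imaging deliberately continues when progression is clinical only. Making an open-label clinical judgement a failure would change the estimand and would not address credit for other therapy.

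Nor do the DCR and PFS treat the patient in opposite ways: censoring also records no failure. The rules differ, and one is missing.

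The size is also open to challenge. Patients qualify only if they start new therapy before RECIST progression and are still free of it at the scan. Those with functioning syndrome must also meet the symptom and marker conditions, although other therapy can improve those too. Table 1 lists low control rates for chemotherapy, and for debulking it reports symptoms only. These points limit the likely size; they do not supply the rule.

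**Conclusion.** The concern holds as a gap in the primary and 3-month DCR definitions that, read literally, biases a single-arm rate upward. It should be closed before results are known.

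The arithmetic effect is certain: 4.5 points for each such patient. The effect on the error rate is illustrative. With true control at 40% and 3%, 5% or 10% of failures reclassified, the chance of 13 or more successes goes from 5.5% to 7.8%, 9.6% or 15.4%, and of 14 or more from 2.1% to 3.2%, 4.2% or 7.4%. Both the frequencies and the cut-offs are assumptions. The documents do not support saying that the trial's error rate is inflated by any particular amount. Nor do they show how the placebo-arm 40% handled new therapy, so the effect on comparability with H0 cannot be judged.

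**What to change.** State in both DCR definitions and in the Statistical plan that a patient who starts any non-protocol anticancer therapy (systemic, liver-directed, radionuclide or surgical) before the DCR assessment counts as not controlled and stays in the denominator, whatever a later scan shows and whether or not one is done.

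Report the DCR that ignores later therapy as a sensitivity analysis. Stopping for clinical progression without new therapy should not by itself be a failure in the primary radiological DCR; counting it as one can be a further sensitivity analysis.

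This is an analysis rule and changes nothing in patient management. N stays at 22. The reported DCR may be slightly lower. The start date and type of any new therapy must be recorded: the data list under Study design names previous treatments only, so it cannot be assumed that later ones are captured. The PFS rule already requires knowing that new treatment began, so the added burden is small.
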